### **7.2 Monitoring AEs**

All AEs will be assessed by the Investigator and recorded including, but not limited to, the following: the event term, the date of onset and resolution, seriousness, severity, relationship to study drug(s), outcome, treatment of the event, and action taken with the study drug(s). Adverse events will be reported starting immediately after the patient has been administered the first dose of study drug(s) until 60 days after the last dose of study treatment, unless the patient withdraws consent to treat, initiates new anti-cancer therapy, is lost to follow up, or death occurs, whichever comes earlier.

An event occurring after the patient has provided informed consent, but before the first dose of study treatment, will be collected as medical history unless the event is either new and attributed to protocol-mandated procedures by the Investigator or there is a significant change in the rate of occurrence or an increase in the severity of the pre-existing condition which is judged to be clinically important and attributed to the protocol-mandated procedures by the Investigator.

Under the latter 2 circumstances, the event will be considered an AE and will be captured as such.

Example 1:

*Thrombophlebitis associated with a blood draw for assessments required prior to dosing per protocol is an event that is related to protocol-mandated procedures. In this scenario, the event of “thrombophlebitis” will be captured as an AE, and it will be documented as being “unrelated” to study drug(s) as applicable.*

Example 2:

*An ankle sprain following an unexpected fall from a flight of stairs while at home, after the patient has provided informed consent, but before the first dose of study drug(s), is clearly unrelated to any protocol-mandated procedures and would therefore be captured as medical history.*

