**Table 1: Schedule of Visits and Assessments – Phase 1b (CRC and HNSCC; NKTR-255 Dose Escalation) (Contd)**

Event a	Screening Period	Treatment Period																		Post-treatment Period				
		Run-in (1 week)			Cycle 1 (21-day cycle)						Cycle 2 (21-day cycle)						Cycle 3 (21-day cycle)			Cycle 4+ (21-day cycles)				
		Day	Day	Day	Day	Day	Day	Day	Day	Day	Day	Day	Day	Day	Day	Day	Day	Day	EOT b	60-day Follow-up c	Survival Follow-up c			
≤ 28d prior to Day 1 of Run-in Period	-7	-6	-4	1	2	3	4	5	8	10	15	1	2	3	4	8	10	15	1	4	8	15		
Windows (days)		+1			+1							+1						+1		+1		+7	±14	Every 3 months ±14 days
General and Safety Assessments																								
ECOG performance status	X	X			X						X						X		X		X		X	
Echocardiogram or MUGA or nuclear scan j	X																				X			
ECG k	X	X			X						X						X				X			
Adverse events review	Continuous from time of ICF until 60 days after last study treatment dose (refer to Sections 7.5 and 7.7)																							
Laboratory Assessments																								
Pregnancy test l	X	X			X						X						X		X		X		X	
Hematology m	X	X	X	X	X	X	X	X	X	X	X	X	X	X	X	X	X	X	X	X	X	X		
Serum chemistry m	X	X		X	X		X	X	X	X		X	X		X	X	X	X	X		X	X		
PT/PTT	X	X			X					X						X		X		X		X	X	
TSH, T4, lipase, amylase, CK n	X	X			X					X						X		X		X		X	X	
Urinalysis	X	X			X					X						X		X		X		X	X	

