### **5.2.3.1 Criteria for Discontinuation from Treatment**

Study treatment may be discontinued for any of the following reasons:

- Any clinical AE, laboratory abnormality, or intercurrent illness that would, in the judgment of the Investigator, affect assessments of clinical status to a significant degree
- Toxicity that, despite maximum medical management, in the judgment of the Investigator, compromises the ability to continue study-specific procedures or is considered to not be in the patient's best interest
- Disease progression (based on Investigator assessment of baseline and post-baseline scans as per RECIST 1.1). In some circumstances patients may be treated beyond disease progression. Details are provided in Section [5.2.5](#).
- Patient request to discontinue treatment for any reason
- Patient noncompliance
- Initiation of systemic antineoplastic therapy other than treatments per protocol in the absence of progression
- Discontinuation of the study treatment at the request of Nektar, a regulatory agency or an institutional review board (IRB) or independent ethics committee (IEC)
- Pregnancy during treatment
- Death
- Investigator's decision, in consultation with the Medical Monitor

If a patient discontinues NKTR-255, the patient may continue on cetuximab alone, at the discretion of the Investigator, until disease progression or initiation of systemic anti-tumor therapy (whichever is earlier).

If a patient discontinues study drug(s), every attempt should be made to continue tumor assessment at every 9 weeks until disease progression or initiation of systemic anti-tumor therapy. The patient will be asked to attend the 60-day post-treatment follow-up assessment visit when discontinuing from the study treatment.

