### **5.2.3.3 Criteria for Discontinuation from Study**

Patients who discontinue study treatment due to any of the treatment discontinuation criteria in Section 5.2.3.1 will continue to be followed for survival per Section 5.2.7.

In the event of an unscheduled study termination by the Sponsor, patients who are on-treatment at the time of the end of the study will be followed for safety for 60 days post EOT as per Section 5.2.6.

Criteria for study discontinuation may include:

- Withdrawal of consent from study
- Loss to follow-up
- Death
- Discontinuation of the study at the request of Nektar, a regulatory agency or an IRB/IEC
- Principal Investigator's decision
- Medical Monitor's assessment due to lack of adherence to protocol

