### **5.2.6 Safety Follow-up**

The Safety Follow-up visit should occur 60 days after the last dose of study treatment unless the patient withdraws consent to treat, initiates new anti-cancer therapy, is lost to follow up, or death occurs. In case of a clinically significant AE, the patient will be followed for safety until resolution, return to baseline values, or permanent sequelae of all toxicities attributable to study drug(s). If the patient discontinues study drug for a clinically significant AE, the patient will be followed until resolution of the AE or until the event is considered to be stable and/or chronic.

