## 7.5 AE Reporting and Follow-up

All AEs, except for SAEs (Section 7.7) and AEs attributed to protocol-mandated procedures (Section 7.2), will be reported from the time of first study drug(s) administration until 60 days after the last dose of study treatment, unless the patient withdraws consent to treat, initiates new anti-cancer therapy, is lost to follow up, or death occurs. All ongoing AEs will be followed until resolution, the patient is lost to follow-up, patient death, or until 60 days after the last dose of study treatment. In case the AE has not completely resolved up to 60 days after the last dose of study treatment or until a new antineoplastic regimen has been initiated, the final outcome of these ongoing AEs will be captured as "Not Recovered/Not Resolved" or "Recovering/Resolving", whichever is applicable.

For specific instructions on identifying and reporting SAEs, see Sections 7.6 and 7.7.

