## 7.7 Serious AE Reporting

Serious AEs occurring after the patient has provided informed consent, but before the first dose of study treatment, will be collected as medical history unless the event is either new and attributed to protocol-mandated procedures by the Investigator or there is a significant change in the rate of occurrence or an increase in the severity of the pre-existing condition which is judged to be clinically important and attributed to the protocol-mandated procedures by the Investigator.

All SAEs, regardless of causality attribution, with an onset within 60 days after the last dose of study treatment (EOT), unless the patient withdraws consent to treat, initiates new anti-cancer therapy, is lost to follow up, or death occurs, will be reported to Nektar Therapeutics Drug Safety within **24 hours** after the site becomes aware of the event.

All AEs and SAEs will be recorded in the electronic case report form (eCRF) database within the timelines outlined in the eCRF completion guidelines. At the time of study start, SAEs may be reported using a paper SAE reporting form. During the study conduct, sites may transition to an electronic SAE (eSAE) system. Nektar or designee will provide training and account information prior to implementing an eSAE system at each site.

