**Treatment-emergent adverse events (TEAE):**

- Any AE that occurs after study treatment initiation.
- An AE that was present at the time of study treatment initiation but worsened after study treatment initiation.
- An AE that was present and resolved prior to treatment and reappeared after treatment initiation.
- Any treatment-related AE will always be considered treatment-emergent.

**NKTR-255 Treatment-emergent adverse events (TEAE) period:** Start of NKTR-255 through 30 days post last dose NKTR-255, or until a new antineoplastic regimen has been initiated, whichever comes first.

**Extended treatment-emergent adverse events (TEAE) period:** Start of any study drug through 60 days post last dose of study drug, or until a new antineoplastic regimen has been initiated, whichever comes first.

**Prior medications:** Prior medications are defined as medications with start date prior to C1D1.

**Concomitant medications:** Concomitant medications are defined as medications with stop date after C1D1, or medications with start date on or after C1D1 and up to 30 days after the last dose of NKTR-255. Medications with a start date after the initiation of any subsequent anticancer treatment will not be considered concomitant medications.

Medications with start date prior to C1D1 and end date after C1D1 will be classified as both prior and concomitant medications.

**Best overall response (BOR):** The BOR is defined as the confirmed best response designation over post-baseline response assessments. Disease assessments beyond progression or after start of subsequent therapy will not be considered for BOR.

**Overall response rate (ORR):** The ORR is defined as the proportion of subjects who have achieved PR or better as their BOR.

**Complete response rate (CRR):** The CRR is defined as the proportion of subjects who have achieved CR as their BOR.

**Responders:** Responders are defined as subjects with a confirmed BOR of PR or better. Ongoing responders are defined as responders who have not progressed, not died, not been off study and not started a subsequent therapy.

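### Reporting of new AEs and SAEs ends when a patient withdraws consent to treatment, an undefined trigger that conflicts with the protocol's own safety follow-up of patients who stop drug but stay on study

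*Protocol*

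**What the plan says.** **Where collection ends.** Protocol 7.2 reports AEs from first dose to 60 days after the last dose, "unless the patient withdraws consent to treat, initiates new anti-cancer therapy, is lost to follow up, or death occurs, whichever comes earlier". Section 7.5 repeats the exception, and 5.2.6 applies it to the 60-day safety visit. Section 7.7 applies it to SAEs starting within 60 days of the last dose: "unless the patient withdraws consent to treat, initiates new anti-cancer therapy, is lost to follow up, or death occurs, will be reported" to the sponsor within 24 hours.

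**How the protocol separates treatment from study.** Section 5.2.3.1 lists a patient's request to stop as a reason to discontinue treatment, and adds: "The patient will be asked to attend the 60-day post-treatment follow-up assessment visit when discontinuing from the study treatment". Section 5.2.3.3 lists "Withdrawal of consent from study" among the reasons for leaving the study. Section 5.2.3 says safety and survival follow-up continue after a patient's withdrawal, and 5.2.3.2 has discontinued patients complete the end-of-treatment visit and the safety follow-up procedures. The AE row of Table 1 reads "Continuous from time of ICF until 60 days after last study treatment dose", then refers to 7.5 and 7.7.

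**How the SAP counts.** SAP 6.6.1 sets the NKTR-255 TEAE period at 30 days after the last NKTR-255 dose. The extended period is "Start of any study drug through 60 days post last dose of study drug, or until a new antineoplastic regimen has been initiated". Neither ends at withdrawal of consent to treat. SAP 6.1 uses the number of subjects in the group as the denominator, and SAP 6.4 does not impute missing values in descriptive analyses.

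**The concern.** The incidence of DLTs and TEAEs is the Phase 1b primary endpoint (SAP 4.1). The four sections tie the end of reporting to a treatment decision, whereas the protocol elsewhere keeps such patients on study. A patient who declines further infusions without progression still has scans about every 9 weeks (5.2.3.1, 8.2) and survival contact every 3 months (5.2.7). Taken literally, the same patient need not have a new SAE reported. Efficacy follow-up would then outlast safety follow-up in a drug-exposed patient who is still in contact with the site.

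Patients may ask to stop because they feel unwell, so the lost time may be informative. The bias would be towards lower TEAE and SAE incidence at the dose levels that are hardest to tolerate.

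**Working it through.** **1. Do the cross-references settle it?** No. Section 5.2.3 promises continued safety follow-up, but by way of 5.2.6, which carries the exception. Table 1 defers to 7.5 and 7.7, which also carry it. Sections 5.2.3.1 and 5.2.3.2 state the follow-up with no consent exception. Section 7.8, in a parallel list of end-points for SAE follow-up, refers to withdrawal of consent without saying whether to treatment or to the study. The protocol therefore supports two readings and does not choose between them.

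**2. What is lost under the literal reading?**

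| Item | After consent to treat is withdrawn |
|---|---|
| New-onset AEs | Not reported (7.2, 7.5) |
| New-onset SAEs | Not reported (7.7) |
| 60-day safety visit | Not required (5.2.6), though 5.2.3.1 asks for it |
| AEs already ongoing | Followed to resolution or 60 days (7.5) |
| Clinically significant AEs | Followed (5.2.6) |
| Unresolved treatment-related SAEs | Follow-up provided for (7.8), subject to its own consent wording |
| Deaths | Captured in survival follow-up (5.2.3.3, 5.2.7) |

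The loss is confined to new-onset events.

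**3. Example of the timing.** Take NKTR-255 on Day 1, last cetuximab on Day 8, and consent to treat withdrawn on Day 10.
- DLT window: 21 − 10 = 11 of 21 days without new-event reporting.
- NKTR-255 TEAE period: Day 1 to Day 1 + 30 = Day 31. Ten of 31 days are reported and 21 are not.
- Tail of the extended period: Day 8 + 60 = Day 68, so 68 − 10 = 58 days are unreported.

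The patient stays in the Safety Population for the whole period, and the crude tables show no new event in that time.

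**4. Size within a dose level.** Dose levels start at 3 patients, and 6 are needed for the RP2D. One patient whose only occurrence of an event is unreported lowers that event's incidence by 1/3 = 33 points or 1/6 = 17 points.

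**5. DLT rate.** The DLT Population takes patients who complete the window or stop because of a DLT (Protocol 9.5, SAP 6.3). Others may be replaced (5.2.3.4). Suppose 2 of 6 patients would have a DLT (33%) and one of the two leaves before it is seen. Excluding that patient gives 1/5 = 20%; a replacement without a DLT gives 1/6 = 17%. The mechanism is selective exclusion.

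**6. Suspension rule.** With posterior Beta(0.66 + x, 1.34 + n − x) and the criterion Pr(rate > 0.33) > 0.95, all 79 boundaries in Table 11 (n = 6 to 84) reproduce. So does Table 12: at a true rate of 0.33, early stopping is 0.211, 0.188, 0.171 and 0.126 against the printed 0.21, 0.19, 0.17 and 0.13, with average sample size 71.8. These figures do not change.

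Table 11 counts safety evaluable patients without defining them. Only if early leavers were kept there as DLT-free would the rule be affected: 5 DLTs in 7 gives 0.967 (suspend), while 5 in 8 gives 0.936 (continue). Assume that 0, 5, 10 or 20% leave inside the window with all their DLTs unseen, an upper bound. The chance of suspension within 30 patients at a true rate of 0.45 is then 0.535, 0.448, 0.363 or 0.216. If half their DLTs are unseen, it is 0.535, 0.491, 0.448 or 0.363. The documents give no such rate and do not say that these patients are kept.

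**The case against.** The strongest reply is that an undefined phrase is being given its worst meaning. Nothing equates consent to treat with a mere request to stop infusions, and 5.2.3, 5.2.3.1 and 5.2.3.2 point towards continued follow-up. The event that made a patient stop would normally already be ongoing, and so would be followed. Section 5.5 sets the DLT window at 21 days with no consent exception, so DLT observation is not expressly cut short. The SAP's TEAE periods are analysis windows and do not mention loss to follow-up either; crude incidence has this weakness whenever follow-up ends early.

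Much of this stands. It rules out three stronger readings that a reader might infer.
- That nothing is collected after withdrawal: ongoing events, clinically significant AEs and deaths still are.
- That Table 1 is an independent contradicting rule: its AE row defers to 7.5 and 7.7.
- That early leavers are counted as DLT-free: the DLT Population excludes them.

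The reply does not remove the inconsistency. The same exception stands in four operative sections, including the one that governs expedited SAE reporting, and a site could follow it in good faith. Unlike loss to follow-up, this loss is avoidable, because the patient is still on study.

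**Conclusion.** The point holds in a limited form. The protocol uses an undefined trigger to end new-onset AE and SAE reporting, and the trigger conflicts with its own provisions for patients who stop treatment but remain on study. If sites apply it literally, unreported time enters the TEAE and SAE tables as no event. For DLTs the risk is informative exclusion from the DLT Population. It is unclear whether a patient who refuses further drug but can still be observed counts as completing the window.

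The overall size cannot be stated, because the documents give no rate of withdrawal of consent to treat, inside the DLT window or at any time. A reader might apply a general discontinuation rate to the DLT rate. That would not be sound: a DLT is missed only if the patient withdraws within 21 days, has a new DLT afterwards, and that DLT goes unreported. The 17 to 33 points above are the effect of one missed event and say nothing about how often it happens. This should be fixed, but it does not undermine the design or any planned figure.

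**What to change.** In 5.2.6, 7.2, 7.5 and 7.7, replace the consent-to-treat exception with withdrawal of consent from the study, citing 5.2.3.3. Align 7.8 and the AE row of Table 1. State that a patient who stops dosing inside the DLT window but remains under observation is observed for DLTs to Day 21 and counts as completing the window. Say in 5.5.4 whether safety evaluable means the DLT Population.

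The SAP says that only Phase 1b patients were enrolled and describes that enrolment as past, so new wording may recover little from them. The clinical study report should therefore give, by dose level, the number of patients whose AE collection ended early for this reason and when it ended, and the number who left the DLT window early, with reasons.

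The cost is mainly wording. The 60-day visit and AE collection are already in place. Sites would collect slightly more AE data, and reported AE rates may be slightly higher.

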### 7.3 Grading of AEs

The severity of an event and the seriousness are not to be considered synonymous. The severity is grading the intensity of an event. The seriousness of an event is based on the patient/event outcome or action criteria. All AEs will be assessed for severity using the National Cancer Institute (NCI)-CTCAE (Version 5.0) guidelines, **CCI**

[REDACTED]. If a particular AE is not listed in the NCI-CTCAE, the following criteria will be used:

- Grade 1 = Mild (event results in mild or transient discomfort, not requiring or needing only minimal intervention or treatment; does not limit or interfere with daily activities [eg, insomnia, mild headache]).
- Grade 2 = Moderate (event is sufficiently discomforting so as to limit or interfere with daily activities; may require interventional treatment [eg, fever requiring antipyretic medication]).
- Grade 3 = Severe (event results in significant symptoms that prevent normal daily activities; may require hospitalization or invasive intervention).
- Grade 4 = Life-threatening or disabling.
- Grade 5 = Death.

AEs will be reported with an individual start and stop date for each level of severity.

## 7.4 Causality Relationship of AEs

The relationship of each AE to each study drug (NKTR-255 and cetuximab) as applicable will be evaluated by the Investigator using the following definitions:

- Not related: The AE is considered not related to the study drug(s). The AE can be reasonably explained by other factors such as the patient's pre-existing medical condition, underlying disease, concurrent illness, or concomitant medications/therapies.
- Related: The AE is considered related to the study drug(s). A plausible temporal sequence exists between the time of administration of the study drug and the development of the AE, or it follows a known response pattern to the investigational product. The AE cannot be reasonably explained by the known characteristics of the patient's clinical state or other concomitant therapies or interventions administered to the patient.

## 7.5 AE Reporting and Follow-up

All AEs, except for SAEs (Section 7.7) and AEs attributed to protocol-mandated procedures (Section 7.2), will be reported from the time of first study drug(s) administration until 60 days after the last dose of study treatment, unless the patient withdraws consent to treat, initiates new anti-cancer therapy, is lost to follow up, or death occurs. All ongoing AEs will be followed until resolution, the patient is lost to follow-up, patient death, or until 60 days after the last dose of study treatment. In case the AE has not completely resolved up to 60 days after the last dose of study treatment or until a new antineoplastic regimen has been initiated, the final outcome of these ongoing AEs will be captured as "Not Recovered/Not Resolved" or "Recovering/Resolving", whichever is applicable.

For specific instructions on identifying and reporting SAEs, see Sections 7.6 and 7.7.

## 7.6 Serious AE Definition

An SAE is defined as any untoward medical occurrence that at any dose:

- Results in death.
- Is life-threatening, ie, in the opinion of the Investigator, the AE places the patient at immediate risk of death from the event as it occurred; it does not include a reaction that, had it occurred in a more severe form, might have caused death.
- Requires inpatient hospitalization or prolongation of an existing hospitalization.

Note: the following are not considered SAEs:

- A surgery or procedure that was planned before the patient entered the study and which is part of the planned study procedure
- Nonmedical reasons, in the absence of an AE

- A visit to the emergency room or other hospital department for less than 24 hours that does not result in admission (unless considered an important medical or life-threatening event)
- Results in persistent or significant disability or incapacity
- Is a congenital anomaly or birth defect
- Is an important medical event that, based upon appropriate medical judgment, may jeopardize the patient and may require medical or surgical intervention to prevent one of the other outcomes listed above

Death is an outcome of an AE and not an AE in itself. All events leading to death, regardless of relationship to study drugs, that occur during the protocol-specified reporting period, must be reported with the exception of deaths attributed to disease progression (Section 7.9). An efficacy failure is not considered an SAE. “Life threatening” means that the patient was at immediate risk of death from the event as it occurred. This does not include an event that might have led to death if it had occurred with greater severity. The Investigator should attempt to establish a diagnosis of the event based on signs, symptoms, and/or other clinical information. In such cases, the diagnosis will be documented as the AE and/or SAE and not the individual signs/symptoms.

